**Study Title:** Storytelling Narrative Communication Intervention for Smoking Cessation in Women Living with HIV

**NCT Number:** NCT03289676

**Date:** 01/10/2018

**Data Analysis:** Data analysis will be done in collaboration with the **U54 Research Design and Analysis Core**. Prior to data entry, data will be reviewed and double-checked for completeness and coding errors first by a research assistant and then by a data manager. An intention-to-treat analysis strategy will be used for cessation outcomes with missing values.

**Specific Aim 1:** Identify storytelling narrative communication (SNC) intervention components that are rated high in transport and identification\* for use as an enhancement to an HIV-tailored smoking cessation intervention (\*Narrative Understanding, Attentional Focus, Narrative Presence, and Emotional Engagement). Through two local networks of Black WLHIV in which [name] is a key collaborator, we will identify volunteers who have quit smoking and film them while they tell their story of quitting. We will ask them structured questions based on Bandura's Self-Efficacy Model to elicit the story components. When the film is edited effectively for clarity of content and length, it will be tested for acceptability using a mix-methods approach. Using focus groups the film will be shown and participants will be asked what they liked the most and the least about the film. These data will be analyzed for saturation through thematic analyses.

**Specific Aim 2:** Determine the feasibility and acceptability of an SNC intervention for smoking cessation for WLHIV by assessing 1) the rate of **recruitment** and **retention** for feasibility and 2) the degree of **transport** and **identification** for acceptability in the narrative enhancement. We will identify and describe the time to recruitment and any barriers. We will also describe reasons for study refusal and compare refusal rates by age ranges and number of cigarettes smoked per day, using  $\chi^2$  and t-tests. We will compare attrition rates at each follow-up by intervention condition and abstinence status, using Mann-Whitney tests. Subjects will complete an Exit Survey, rating their overall satisfaction with the intervention that they have. They will also rate their experience with the SNC videos, using a 7-point Likert-type scale. In addition, the Measure of Narrative Engagement will be used as a quantitative indicator of 1) narrative understanding, 2) attentional focus, 3) narrative presence, and 4) emotional engagement.

**Specific Aim 3:** Establish an effect size of HIV-tailored smoking cessation and SNC interventions in comparison with the HIV-tailored smoking cessation intervention only for WLHIV by comparing 30-day abstinence rates at 6-month follow-up. We will evaluate the balance of baseline demographics and smoking behavior between the two arms, using t-tests or Mann-Whitney tests for continuous variables and  $\chi^2$  tests for categorical variables. We will examine differences in continuous or 7-day point-prevalence abstinence rates between the two arms, using the  $\chi^2$  tests. Individuals who are not available at follow-up assessments or yield a cotinine test result higher than the cutoff level of 0 (cotinine level 0-30mg/ml) will be all treated as smoking. We will calculate an effect size by comparing 30-day abstinence rates at 6-month follow-up point between the two arms. We will also explore longitudinal logistic regression models under the framework of generalized linear mixed models to examine the relationships between abstinence status and intervention conditions over time.

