Study Title: Storytelling Narrative Communication Intervention for Smoking Cessation in Women Living with HIV

NCT Number: NCT03289676

Date: 01/10/2018

University of Massachusetts Boston Institutional Review Board Protocol

A. Title: Storytelling Narrative Communication Intervention for Smoking Cessation in Women Living with HIV

B. Investigators: [name], RN, University of Massachusetts Boston
 [name], RN, FAAN, Dana-Farber/Harvard Cancer Center
 [name], RN, APHN-BC, FAAN, University of Massachusetts Boston

PROJECT DESCRIPTION

HIV has transformed into a chronic illness due to the advent of effective treatments in the absence of a cure. As a result, the prevalence of non-AIDS defining cancers (NADCs), including lung cancer, has increased three-fold among people living with HIV. NADCs now account for 50% of all cancers among the people. Smoking is one of the major contributing factors to lung cancer and smoking prevalence is substantially higher in this population than the general U.S. population. Smoking prevalence does not differ by gender among people living with HIV. Women of color, particularly African American women represent the majority of women living with HIV (WLHIV) followed by Latinas. WLHIV smoke at a rate almost 3 times higher than that for the general U.S. female population (e.g., 42% vs. 16%). The proposed study has two phases: 1) the development of a storytelling narrative communication (SNC) intervention that will be added to an established HIV-tailored smoking cessation intervention and 2) a two-arm randomized controlled trial (RCT) of the HIV-tailored intervention plus the SNC Intervention compared with the HIV-tailored intervention only. We will develop narrative videos with three to five WLHIV who will be talking about their personal struggles with smoking and success in quitting. Our preliminary study revealed that the established HIV-tailored intervention was effective only for short-term (≤ 2 months) abstinence. Many relapsed to smoking between the 2nd and 6th month of quitting. We propose that the SNC intervention will be an effective strategy to sustain their quit efforts for long-term abstinence (≥ 6 months). A total of 60 WLHIV will be recruited and randomly assigned to either the experimental arm (a combination of HIV-tailored and SNC interventions) or the control arm (HIV-tailored intervention only).

STUDY AIMS

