8. Have at least eight full drops of saliva drip from the tube onto the white padded area of the test strip (right below the three green arrows).

A research staff member will closely monitor the whole process via the video call. She/he will be blind to treatment condition. The person can read the result of the test when the blue line on top of the strip disappears, which usually takes 20-30 minutes. She/he will ask participants to take a photo of the strip right after the video call and send it to her/him. Then, the person will share the photo with other research staff to validate one's reading of the result.

Study Measures and Assessment Procedures: Baseline and three follow-up assessments will be conducted by telephone survey. All measures (see Table 1 below) have been tested and validated for use with WLHIV. Those who report abstinence will receive NicAlert® test kits at 3-month follow-up by a post office mail right before the follow-up assessments. As described above, participants will be guided step-by-step to perform the test while the whole process being closely monitored by research staff via a video call.

Table 1 Assessment schedule of study measures

Variables	Measure	Base	1M*	2 Ms*	3 Ms*
Demographics	Demographic Datasheet	✓			
History of HIV Infection	Year of the diagnosis, CD4 cell count, and viral load	✓			
HIV-medication Adherence	CASE Medication Adherence Scale ⁴⁰	✓			
History of Smoking and Quitting	Smoking and Quitting Datasheet	✓			
Stigma and Secrecy	HIV-related Stigma Scale ⁴¹	✓			
Alcohol Use	Alcohol Use Disorders Identification Test (AUDIT) ³²	✓			
Depression	Patient Health Questionnaire-9 ⁴²	✓			✓
Anxiety	Generalized Anxiety Scale-7 ⁴³	✓			✓
Nicotine Dependence	Fagerström Test for Nicotine Dependence ^{37,38}	✓	✓	✓	✓
Self-Efficacy	Self-Efficacy Scale ⁴⁴	✓	✓	✓	✓
Nicotine Withdrawal	Minnesota Tobacco Withdrawal Scale ³⁶		✓	✓	✓
Narrative Engagement	The Measure of Narrative Engagement ¹⁹			✓	✓
Program Evaluation	The Client Satisfaction Questionnaire ⁴⁵		✓	✓	✓
Abstinence or Cigarette Consumption	7-day Timeline Follow-back Smoking Behavior ³⁵		✓	✓	✓
	Saliva Cotinine Test (NicAlert®)				✓
Treatment Fidelity	Intervention Fidelity and Competence Scale ([name], unpublished work)		✓	✓	✓

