Power and Sample Size: This study aims to establish a preliminary effect size. In the currently ongoing study, abstinence rate for the video arm was 75.5% at post-quit 1 month but dropped to 20.0% at post-quit 3 months. For a two-sided test at a 5% significance level, 52 participants are required per arm to have 80% of power for abstinence rates 45.5% vs. 20%.⁴⁶ As a pilot study, we will recruit 50 subjects (25 per arm).

Data Analysis: Data analysis will be done in collaboration with the **U54 Research Design and Analysis Core**. Prior to data entry, data will be reviewed and double-checked for completeness and coding errors first by a research assistant and then by a data manager. An intention-to-treat analysis strategy will be used for cessation outcomes with missing values.

Specific Aim 1: Identify storytelling narrative communication (SNC) intervention components that are rated high in transport and identification* for use as an enhancement to an HIV-tailored smoking cessation intervention (*Narrative Understanding, Attentional Focus, Narrative Presence, and Emotional Engagement). Through two local networks of Black WLHIV in which [name] is a key collaborator, we will identify volunteers who have quit smoking and film them while they tell their story of quitting. We will ask them structured questions based on Bandura's Self-Efficacy Model to elicit the story components. When the film is edited effectively for clarity of content and length, it will be tested for acceptability using a mix-methods approach. Using focus groups the film will be shown and participants will be asked what they liked the most and the least about the film. These data will be analyzed for saturation through thematic analyses.

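### Aim 3 ties its effect size to a 30-day, 6-month outcome that the schedule never collects, and the only other abstinence comparison names no visit and no single definition, so the reported effect can be chosen after the data are seen

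*SAP*

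**What the plan says.** Specific Aim 3 is worded alike in the protocol's Data Analysis section and in the SAP. It says twice that the effect size will come from comparing 30-day abstinence rates at a 6-month follow-up. Between those two statements stands a separate chi-square comparison: "We will examine differences in continuous or 7-day point-prevalence abstinence rates between the two arms". That sentence names no visit, gives no order between the two definitions and does not define continuous abstinence. The next sentence counts women who are unavailable, or whose cotinine exceeds the cutoff, as smoking. A mixed logistic model over time is added as something to explore.

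The protocol's Study Measures section says: "Baseline and three follow-up assessments will be conducted by telephone survey". Table 1 places these at 1, 2 and 3 months. Its smoking measures are the 7-day Timeline Follow-back at all three and saliva cotinine at month 3 only. Research Design (Phase 2) and Video Watching both call the 3-month post-quit visit the last one, and control women receive the smoking-cessation videos straight after it.

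Power and Sample Size says "This study aims to establish a preliminary effect size" and "As a pilot study, we will recruit 50 subjects (25 per arm" in total. The Study Aims section says the effect size is meant for later grant applications.

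**The concern.** Aim 3 has one product, an effect size on which a later trial would be planned. The contrast named to supply it has no visit and no instrument behind it. A substitute must be found, and the one remaining abstinence sentence offers alternatives without ranking them. With 25 women per arm, different definitions and months can easily give different answers. If the choice is made after the results are visible, the most favourable contrast is likely to be carried forward. The reported effect would then be biased upward and the next trial would be too small.

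**Working it through.** **1. Can the named effect size be obtained?** It needs an assessment at 6 months and a measure covering 30 days. The last assessment is at 3 months, and the only look-back instrument covers 7 days. Neither element is scheduled, so it cannot.

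**2. What can replace it?** Two readings of the chi-square sentence are available.
- Narrow: the cotinine rule follows directly and cotinine exists only at month 3, so the sentence may mean the two definitions at month 3. That is two contrasts.
- Broad: smoking is recorded at three visits, giving 7-day prevalence at months 1, 2 and 3, plus abstinence at every visit through month 2 and through month 3. That is five contrasts, because at month 1 the two definitions coincide.

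**3. The plan's own figure.** The protocol states "For a two-sided test at a 5% significance level, 52 participants are required per arm" "to have 80% of power for abstinence rates 45.5% vs. 20"%. With pooled rate (0.455 + 0.20)/2 = 0.3275:

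n = [1.960·√(2·0.3275·0.6725) + 0.8416·√(0.455·0.545 + 0.20·0.80)]² / 0.255² = (1.3008 + 0.5376)² / 0.0650 = 51.97, so 52 per arm.

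The figure reproduces as one two-sided 5% test. This confirms the sample-size calculation only; it sets no alpha for Aim 3. Power at 25 per arm is 48.4%.

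**4. How much can choosing matter?** Simulation with 25 per arm and no true difference:
- Each woman has three standard normal values with common correlation ρ. She is abstinent at visit j if her value lies below Φ⁻¹(pⱼ). Continuous abstinence means abstinent at every visit so far.
- Rates at months 1, 2 and 3 are 75.5/45/20% or 50/35/20%. The 75.5% and 20% come from Power and Sample Size; the other rates, and ρ from 0.3 to 0.9, are assumptions.
- The test is the uncorrected chi-square, d²/[2p̄(1 − p̄)/25] > 3.84, where d is the arm difference and p̄ the pooled rate. There were 40,000 trials per setting.

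Results for 75.5/45/20%:

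| ρ | Any p<0.05, two at month 3 | Any p<0.05, five | Mean largest difference, two | Mean largest difference, five |
|---|---|---|---|---|
| 0.3 | 8.8% | 20.3% | 3.1 points | 10.7 points |
| 0.5 | 8.5% | 19.4% | 2.5 points | 10.0 points |
| 0.7 | 7.4% | 17.7% | 1.7 points | 9.2 points |
| 0.9 | 5.9% | 14.8% | 0.4 points | 8.1 points |

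The mean largest difference is in favour of the storytelling arm. Over both rate sets:
- two contrasts: about 6 to 9% and 0.4 to 4 points;
- five contrasts: about 15 to 21% and 7.5 to 11 points.

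A single fixed month-3 contrast gives about 5.5% and an average of zero. With five contrasts, a difference of 20 points or more in favour of the storytelling arm appears in 18 to 23% of trials, against about 5% for the fixed contrast. With a continuity correction, the five-contrast chance of any p<0.05 falls to about 6 to 9%.

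**5. Precision of one fixed contrast.** At the planning rates, the 95% half-width is 1.96·√(0.455·0.545/25 + 0.20·0.80/25) = 1.96·0.1278 = 25.0 points, around a planned difference of 25.5 points.

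**The case against.** The strongest reply is that the plan does fix the effect size: Aim 3 says twice which contrast supplies it, and the chi-square sentence is a separate item. That is right on paper. A reader who infers that the documents leave the effect size open overlooks those statements. They give no protection in practice, though, because the contrast they name is never measured.

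A reader might also infer that several tests compete at the full 5% level and that the trial's error rate is inflated. The documents do not support this. The SAP sets no alpha for Aim 3. The 5% stands only in a calculation for 52 per arm that this pilot says it will not meet, and no decision depends on significance.

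Nor do the documents say that chi-square tests will be run at each visit. The five-contrast count is one reading, and the two month-3 definitions are an equally fair one, with much smaller figures. The type of chi-square is also unspecified, and a continuity correction lowers the false-positive figures.

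What remains does not depend on alpha. The trial's product is an effect size, and selection biases it whether or not anything is tested.

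**Conclusion.** The point holds as a contradiction between endpoint and schedule that leaves room for selective reporting. Aim 3's named effect size is unobtainable, and no obtainable contrast is designated in its place. It does not hold as a claim of a breached family-wise error rate.

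The size depends on how many contrasts are really in play. The average spurious benefit is modest if only the two month-3 definitions compete. If all five do, it is a substantial fraction of the planned difference: 7.5/25.5 = 29% to 11/25.5 = 43%. These figures assume no true effect, that the largest favourable difference is always the one reported, the stated correlations, and the month-2 rates and the 50% month-1 rate, none of which the documents give. They also take 25 per arm from Power and Sample Size; the Project Description's total of 60 is a separate inconsistency. That the named contrast cannot be computed rests on no assumption. This should be corrected before any outcome data are examined.

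**What to change.** In Aim 3 of both documents, replace the two 30-day, 6-month statements and the either/or phrase with one contrast: 7-day point-prevalence abstinence, cotinine-verified, at 3 months post-quit. State that it is the sole source of the effect size and will be reported as a difference between arms with a 95% confidence interval. It uses the scheduled instrument at the only biochemically verified visit. It also matches the time point of the 20% in the power statement, although that statement gives no definition of abstinence.

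Report continuous abstinence (with a definition), the month-1 and month-2 comparisons and the mixed model in full, labelled exploratory. Changing only the either/or phrase would not be enough, because Aim 3 would then name two sources for the effect size.

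The cost is a few sentences in each document, with no new visits, data or participants. There are two small downsides. A favourable result on another definition or visit can no longer be presented as the trial's effect. The trial also makes no claim about abstinence at 6 months or longer, which the Project Description gives as the intervention's goal. Keeping the 6-month outcome instead would need a new visit and a 30-day measure, and the comparison would fall after control women have been sent the cessation videos.
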